Multi-centre prospective observational study of diagnosis, management and outcome in a large cohort of pregnancies affected by abnormal fetal brain development.

The study is designed to include all developmental brain abnormalities identified by ante-natal ultrasound screening from 18 weeks gestation onwards. Participants are recruited from at least 13 sites within the UK incorporating a wide geographic and socioeconomic base. MR scanning is then carried out either in a primary unit (Sheffield) or in one of five secondary units (Newcastle, Leeds, Birmingham, Belfast and Manchester). Figure 1 outlines the study design and length of time that each participant may remain in the study process.

Figure 1. MERIDIAN study design

Primary Outcomes

- 1) Absolute diagnostic accuracy of MR as assessed by percentage of cases where in utero MR diagnosis agrees with post-mortem autopsy/MR or postnatal imaging.
- 2) Absolute diagnostic accuracy of US as assessed by percentage of cases where US diagnosis at the time of referral for MR agrees with post-mortem autopsy/MR or postnatal imaging.

Agreement between prenatal diagnosis (both before and after MR) and outcome diagnosis will be judged by an appointed independent expert panel consisting of a fetal medicine clinician, paediatric neuroradiologist and paediatric neurologist or neurosurgeon.

Secondary Outcomes

Effect of including MR scan on diagnostic confidence

Change in diagnostic confidence will be measured before and after the MR scan as assessed by a 5 point Likert scale.

Effect of including MR scan on prognosis

Change in prognosis will be measured before and after the MR scan as assessed by a 4 point categorical scale (poor – less than 50% chance of normal neuro-developmental outcome, intermediate - 50-90% chance of normal outcome, favourable - greater than 90% chance of normal outcome, normal – no abnormality found after detailed fetal medicine investigation).

Effect of including MR scan on management

Change in management will be measured before and after the MR scan as assessed by a 2 point categorical scale. This scale will record whether termination of pregnancy was discussed on the basis of poor neuro-developmental prognosis.

4. Ancillary sub-studies

Sociological Study

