Where it is not possible to arrange a face to face appointment, or if for any reason the questionnaires are not completed during the appointment then there will be the option for the GMFCS questions (adapted for parent completion) and SDQ to be posted out or given to parents for them to complete and return to the research team. Alternatively the questionnaires can be completed over the telephone with the child's parent.

The research team will categorise the children as severely impaired (scoring <70), mild-moderately impaired (scoring 70-85) or normal (scoring 85+) based on the results of the developmental assessments. These categories will be used to complete the developmental assessment CRF.

After the developmental assessments all participants will be debriefed via a feedback letter from the research team, which will contain details of the results from the developmental assessment. Where an important previously unrecognised disability has been identified, we will speak to parents about future actions. Typically this would include informing the GP and advising about appropriate referrals either to community paediatrics or therapy services. A member of the study team (NE, an experienced paediatrician) would be available for discussion and advice if the best course of action was not immediately apparent.

Project 3

There is no input required from the MERIDIAN participants or research sites for completion of project 3. Project 3 will be completed by the central study team at the University of Sheffield.

[figure not shown]
The information for project 3 will come from the assessments described in project 2. We will identify all cases of isolated mild ventriculomegaly diagnosed on iuMR and define their developmental outcome at 2-3 years as severely impaired, mild-moderately impaired or normal as per project 2. In MERIDIAN, the most common information given to women on the basis of isolated mild VM on USS is "favourable (90%)" followed by poor or intermediate and the remainder as normal.

We will calculate the prevalence of severe and non-severe impairments in isolated mild VM cases.

Please see Figure 2. for details of procedures and data collection document

Figure 2. Procedure for MERIDIAN 2-3 year follow up study

Screening

Project 1 – Case note review

Project 1 and 2 – Case note review and BSID

Project 1
If consented to project 1 only research midwife will conduct medical case note review and record details of any further follow up

Project 1 and 2

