The first consideration is a pre-cursor to the second, since the comparison in 2) is irrelevant if neither MR nor USS contain some measure of useful prognostic information. We will quantify 1) by assessing the concordance between severe neurodevelopmental impairment (BSID score of <80 on the Cognitive AND language index or a combined score of <85 or a motor score of <70) and poor prognosis, based on i) MR and ii) USS. The sensitivity, specificity, positive and negative predictive values of MR and of USS will be reported.

The second consideration is to compare the relative prognostic accuracy of USS and MR. We will do so by calculating the difference in the respective sensitivities and specificities using the paired sample methods recommended by Newcombe [18].

	Outcome	
	Severe impairment (BSID<70) N=xxx	No severe impairment (BSID>=70) N=xxx
USS prognosis		
Poor	n (%)	n (%)
Normal/favourable	n (%)	n (%)
% correctly classified*	$P_{sens (USS)}$	$P_{spec (USS)}$
MR prognosis		
Poor	n (%)	n (%)
Normal/favourable	n (%)	n (%)
% correctly classified*	$P_{sens (MR)}$	$P_{spec (MR)}$
Difference (95% CI)	$P_{sens (MR)} - P_{sens (USS)}$	$P_{spec (MR)} - P_{spec (USS)}$
P-value (McNemar)		

* Here, we consider "Correct" to mean 1) Poor prognosis corresponds to severe impairment, and 2) Normal/favourable prognoses correspond to no severe impairment. The percentages correctly classified reflect 1) sensitivity and 2) specificity respectively.

The secondary outcomes are

- 3) To assess qualitatively the cases for which the USS prognosis and MR prognosis differed, in relation specifically to the original diagnoses
- 4) To look at the concordance in the subgroup of children for which the MR scan was performed within 24 weeks
- 5) To assess ability to predict non-severe impairment

The last of these will further subdivide children without severe impairment (BSID>=70) into "mild-moderate impairment" (BSID between 70 and 85) and "Normal" (BSID>85). The corresponding prognostic categories are "Intermediate" and "Normal or Favourable", and the concordance between the three prognostic categories and the three outcomes will be reported by two-way tabulations.

Sample size Project 2

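### Project 2 scores a prognosis defined as the chance of a normal outcome as if it graded severity, which caps Intermediate concordance at 50% and makes some apt poor calls false positives

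*Protocol*

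**What the plan says.** **Main protocol, section 3 (Study Design), Secondary Outcomes.** Prognosis is recorded before and after MR in four categories. Three are bands for a single probability: "poor – less than 50% chance of normal neuro-developmental outcome", "intermediate - 50-90% chance of normal outcome" and "favourable - greater than 90% chance of normal outcome". The fourth, normal, is for fetuses in whom no abnormality was found. No category grades severity. The follow-up protocol keeps these labels: section 6, Project 3, says that the commonest information given for isolated mild ventriculomegaly was favourable, "followed by poor or intermediate and the remainder as normal".

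**Follow-up protocol, section 7 (Statistics), Analysis of Project 2.** The primary table has two outcome columns, severe impairment and no severe impairment. Its footnote defines correct as "Poor prognosis corresponds to severe impairment, and 2) Normal/favourable prognoses correspond to no severe impairment" and continues: "The percentages correctly classified reflect 1) sensitivity and 2) specificity respectively". These percentages are compared between MR and US with paired confidence intervals and McNemar's test. A secondary analysis splits the non-severe children at BSID 85 and names Intermediate as the prognosis corresponding to mild-moderate impairment; "the concordance between the three prognostic categories and the three outcomes will be reported by two-way tabulations".

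**Severe is defined in two ways.** The table header in section 7, and section 6 (Project 2), use a score below 70. The text of sections 2 and 7 uses cognitive and language indices below 80, or a combined score below 85, or a motor score below 70. The full lists in those sections add cerebral palsy on GMFCS and an ASQ rule.

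**The concern.** A clinician who records poor has said that a normal outcome is less likely than not, and nothing about how severe an abnormal outcome would be. A clinician who records intermediate has said that a normal outcome is at least as likely as not. Project 2 reads the first as a forecast of severe impairment and the second as a forecast of mild-moderate impairment. No section reconciles the two readings.

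Two results are at stake. Low agreement in the Intermediate row of the three-way table could be taken for poor prognostic skill when it follows from the definition. In the primary comparison, a call that was right on the recorded scale can lower specificity. If US says favourable, MR says poor and the child is mild-moderately impaired, the table credits US and charges MR.

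**Working it through.** **1. The plan's own figure.** Sample size Project 2 states 90% power with 400 cases for +20 points of sensitivity and +10 points of specificity, two-sided 5%. The protocol gives neither the prevalence of severe impairment nor the discordant proportion ψ, so this can only be bracketed. The paired formula is n = (1.96√ψ + 1.2816√(ψ − d²))² / d².
- ψ = 200/832 = 0.24 (almost 200 changed prognoses over the 832 scanned): 59 severe (d = 0.20) plus 248 non-severe (d = 0.10), 307 in all. This fits 400 cases if severe prevalence lies between 59/400 = 15% and 1 − 248/400 = 38%.
- ψ = 0.35: 88 + 364 = 452, more than 400.

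The figure is neither confirmed nor refuted, and the present point does not depend on it.

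**2. Intermediate row, from the definition alone.** Take normal to mean the same in both documents. In a perfectly calibrated Intermediate group the expected proportion normal is between 0.50 and 0.90.
- Share that is mild-moderate ≤ 1 − P(normal).
- At P(normal) = 0.50 the ceiling is 50%; at 0.90 it is 10%.
- Any severe outcome in the group lowers it further.

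So at least half of a correctly graded Intermediate group, and possibly 90% or more, falls off the diagonal. This is the percentage within the prognostic category; the plan names no summary statistic for the table.

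**3. Poor calls in the primary table.** A child certain to be mild-moderately impaired has P(normal) = 0, so the main protocol's scale requires poor. The child sits in the no-severe-impairment column, where only Normal/favourable is scored correct. The call that fits the scale is therefore a false positive.

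**4. How this depends on the definition of severe.** Let s be the share of not-normal outcomes that count as severe. The following is an illustration with assumed inputs: 400 children, perfectly calibrated, with 80 Poor at P(normal) = 0.30, 120 Intermediate at 0.70 and 200 Favourable at 0.95. Intermediate is counted as not poor, because the primary table has no row for it.
- Normal: 24 + 84 + 190 = 298. Not normal: 56 + 36 + 10 = 102.
- Specificity against not normal: (298 − 24)/298 = 91.9%.
- Specificity against severe: 1 − (80 − 56s)/(400 − 102s).

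| s | Specificity against severe | Share of Poor scored correct (56s/80) |
|---|---|---|
| 0.2 | 81.9% | 14% |
| 0.5 | 85.1% | 35% |
| 0.8 | 88.9% | 56% |
| 1.0 | 91.9% | 70% |

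The shortfall in specificity is about 10, 7 and 3 points at s = 0.2, 0.5 and 0.8, and nil at s = 1. Sensitivity is 56/102 = 54.9% throughout. A cut at 70 means a lower s. The text rule pushes s towards 1, since a combined score of 70-84 is then already severe; what remains is narrow, such as a motor score of 70-85 alone.

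At s = 0.5 the 80 Poor children are 28 severe, 28 mild-moderate and 24 normal. The 24 would be errors under any dichotomy. Only the 28 come from the mismatch.

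**5. Ceiling on the cost to MR.** Each non-severe child moved by MR from favourable to poor costs MR 1/n(non-severe) of specificity relative to US. The plan reports 38 changes to the poorest prognosis in the whole cohort; scaled, 38 × 400/832 ≈ 18. If all 18 were mild-moderate and had been favourable on US, with an assumed 280 to 340 non-severe children, the cost is 18/340 = 5.3 to 18/280 = 6.4 points, against the +10 in the power statement. This is an extreme, not an estimate, and it ignores moves in the other direction.

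**The case against.** **Severe impairment is a legitimate target.** Section 2 of the follow-up protocol states the aim as concordance between severe impairment and poor prognosis, and a test may be evaluated against a target that its label does not name. This stands: the choice of primary outcome is not an error.

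**The rule is the same for both tests.** A reader might infer that the scoring is biased against MR. The documents do not support that. If US says poor, MR says favourable and the child is mild-moderately impaired, the rule credits MR. The sign of the net effect depends on cross-classified counts that the protocol does not give.

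**Dichotomising any probability makes errors.** A reader might also infer that every miss by a calibrated rater comes from this mapping. It does not: poor calls in children who turn out normal would be misses against a normal/not-normal target too.

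**Under the text definition the primary-table effect mostly disappears.** This also stands, but the table header says otherwise, so the size is open until the definitions are reconciled.

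**Much of the remedy is already planned.** The three-way table contains the proportion normal per category, and predictive values and the range of scores are also planned. True, but none of these is set against the stated bands, and the footnote and the Intermediate pairing still tell the reader what counts as right.

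**Conclusion.** The point holds in a limited form. The recorded prognosis is a probability band for a normal outcome, and Project 2 scores it as a severity grade.

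The firm result is in the secondary table: concordance of Intermediate with mild-moderate impairment cannot exceed 50% for a perfectly calibrated rater, and is at or below 10% at the top of the band. This needs only the main protocol's definition and the assumption that normal means the same in both documents.

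In the primary table, poor calls in children who are neither normal nor severe are false positives. The effect is potentially large under BSID below 70 and small under the text rule; the illustrated 3 to 10 points of specificity rest on assumed case mix. A warning recorded as Intermediate cannot be assessed, because that table does not say how Intermediate is scored.

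It is not shown that the MR-US difference is biased in either direction, nor that severe impairment should give up its place as primary target.

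**What to change.** In section 7 of the follow-up protocol, or in the analysis plan:

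1. Keep severe impairment as the primary target, but call the analysis prediction of severe impairment. Replace the correctly-classified label and its footnote with plain sensitivity and specificity of a poor prognosis for severe impairment.
2. Drop the correspondence between Intermediate and mild-moderate impairment. Keep the three-way table as description.
3. For MR and for US separately, report the observed proportion with a normal outcome in each prognostic category, with a 95% confidence interval, beside the main protocol's bands (below 50%, 50-90%, above 90%). State that normal means the follow-up protocol's own category (BSID 85 or above), since the main protocol does not define it.
4. Add a secondary paired comparison of sensitivity and specificity on normal versus not normal, with poor as test-positive. Not normal should include mild-moderate impairment, all the severe criteria listed in section 7 (so that children with only ASQ or GMFCS data are placed) and the non-survivors counted as poor outcomes under Sample size Project 2, with terminations handled by the expert panel as already planned.
5. Reconcile the two definitions of severe, since they determine how much the primary table is affected.

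The cost is wording and slightly more analysis; the prognosis and outcome data are already to be collected. The added comparison is not covered by the Project 2 power statement and should be reported as such.

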Our sample size is constrained by the original MERIDIAN cohort, but our data collected to date provides some assurance that we will have adequate power to address the primary outcome defined by this project. As well as approaching all children known to have survived (expected number approximately 500), our analysis will include non-surviving infants (defined as having had poor outcomes; expected number approximately 50-100). Allowing for attrition in the surviving child group we approximate that there will be 400 cases, from data collected in the entire cohort, there are almost 200 instances where prognosis changed as a result of MR imaging, of whom 38 are now classified as the poorest prognosis. Scaling these prevalence's down, 400 cases will have a 90% power to detect a 20% increase in the sensitivity and a 10% increase in specificity using the tests outlined above at a two-sided significance level of 5%.

We will quantify the impact of selective participant retention by comparing prognoses and diagnoses of consenting participants with those who refused. Non-surviving fetuses or children will by definition have no BSID outcome data, but will be included in the primary analyses as having poor outcomes. Outcomes among fetuses for whom TOP was performed are controversial, but some diagnoses (for example TOP for anencephaly) are inevitably fatal. For these cases we will use our existing independent expert panels to adjudicate whether, and how, the data should be included.

Hypothesis

The clinical significance of fetal brain abnormalities are more accurately predicted by MR imaging when compared with USS. Specifically, we predict a 10% improvement in prognostic accuracy by using MR imaging.

Analysis of Project 3

Using the categories detailed in project 2 (severely impaired, mild-moderately impaired and normal) we will calculate the prevalence of severe and non-severe impairments from our data, together with exact binomial confidence intervals and compare this to the prognoses obtained from cases where USS identified isolated mild VM. Where prognosis changed as a result of MR imaging we will assess whether this was attributable to the MR identifying further diagnoses.

Sample size Project 3

With approximately 140 cases and assuming the prevalence of poor outcome is indeed less than 10%, we will be able to estimate the prevalence to within a standard error of 2.5%.

Hypothesis

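### Project 2 pools non-survivors with only the 60-80% of survivors expected to be assessed and describes no adjustment, so the predictive values of a poor prognosis depend on survivor turnout

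*Protocol*

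**What the plan says.** All references are to the 2-3 year follow-up protocol, section 7 (Statistics), unless noted.

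- **Survivors.** Sample size Project 2 speaks of "approaching all children known to have survived (expected number approximately 500"), and then: "Allowing for attrition in the surviving child group we approximate that there will be 400 cases".
- **Non-survivors.** The same section adds that "our analysis will include non-surviving infants (defined as having had poor outcomes; expected number approximately 50-100"), and later: "Non-surviving fetuses or children will by definition have no BSID outcome data, but will be included in the primary analyses as having poor outcomes". Section 4 (Selection and withdrawal) says that for children who have died only the date and cause of death are recorded and the family is not contacted.
- **Terminations.** These are set apart. The expert panels decide whether and how each is used.
- **Measures.** Analysis of Project 2 says: "The sensitivity, specificity, positive and negative predictive values of MR and of USS will be reported". Its table shell uses raw counts and percentages. MR and USS are compared through paired differences in sensitivity and specificity.
- **Safeguard.** Selective retention is to be examined by comparing the prognoses and diagnoses of consenters and refusers. No weighting or standardisation is described.

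**The concern.** Whether a case enters the analysis depends on its outcome. A death enters once it is identified. A survivor must have agreed earlier to be approached, meet the custody and language criteria, be judged suitable to contact, respond, consent, and be no older than 38 months for a developmental assessment (sections 4 and 5).

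PPV and NPV depend directly on the share of poor outcomes among the cases analysed. If one part of the poor-outcome group enters almost in full and everyone else at 60-80%, that share reflects turnout as well as the cohort.

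Project 2 aims to improve the prognostic information available in pregnancy, and its first primary consideration is the value of each prognosis. The PPV of a poor prognosis is the figure that answers this most directly.

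Comparing consenters with refusers does not help here. If survivors take part at random, the two groups look alike and the pooled PPV is still off.

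**Working it through.** **The plan's own figure.** The plan states that "400 cases will have a 90% power to detect a 20% increase in the sensitivity and a 10% increase in specificity" "at a two-sided significance level of 5" per cent. This cannot be reproduced exactly, because neither the number with severe impairment nor the discordance within outcome groups is given. The McNemar formula is n = (z_a√ψ + z_b√(ψ − d²))² / d². Taking ψ = 200/832 = 0.24 from the changed prognoses in the cohort, d = 0.20 needs 59 severe cases and d = 0.10 needs 248 non-severe cases, so 400 is attainable. At ψ = 0.40 the needs are 101 and 416, and it is not. The power statement is not the problem raised here.

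**Survivor turnout implied by the plan.** The 400 can be read in two ways.
- Survivors only: 400/500 = 80%.
- Including 50 or 100 deaths: 350/500 = 70% or 300/500 = 60%. With 75 deaths, 325/500 = 65%.

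**Inputs for the predictive values.** From the plan: 500 survivors, and deaths D = 75 (middle of 50-100). Assumed, because the plan gives none: 10% of survivors severely impaired; sensitivity 70%, taken as equal in deaths and severe survivors; specificity 90%; participation unrelated to outcome and prognosis.

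**Formulas.** With N survivors assessed and s the proportion severe:
- q = (D + N·s)/(D + N)
- PPV = 0.7q / (0.7q + 0.1(1 − q))
- NPV = 0.9(1 − q) / (0.9(1 − q) + 0.3q)

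| Survivors counted | q | PPV | NPV |
|---|---|---|---|
| All 500 (target) | 125/575 = 21.7% | 66.0% | 91.5% |
| 400 (survivors only) | 115/475 = 24.2% | 69.1% | 90.4% |
| 325 (the 400 include deaths) | 107.5/400 = 26.9% | 72.0% | 89.1% |

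PPV is therefore 3.1 or 6.0 points too high, and NPV 1.2 or 2.4 points too low. Over D = 50, 75, 100, s = 5%, 10%, 15% and both readings of the 400, PPV is about 2 to 9 points too high and NPV about 1 to 4 points too low.

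**Sensitivity.** Pooled sensitivity is (D·p_d + N·s·p_s)/(D + N·s), where p_d and p_s are the proportions given a poor prognosis among deaths and severe survivors. For N = 500 against N = 325 in the same case:
- p_d = 90%, p_s = 50%: 74.0% becomes 77.9%.
- p_d = p_s = 50%: no change.
- p_d = 30%, p_s = 50%: 38.0% becomes 36.0%.

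**Specificity.** Only survivors without severe impairment enter it. Thinning them at random leaves it unchanged.

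**Paired MR-USS sensitivity difference.** Take 100 deaths and 15% severe, so 75 severe survivors in full and 45 at 60% turnout.
- Gain 10 points in deaths, 20 in severe survivors: (10 + 15)/175 = 14.3 becomes (10 + 9)/145 = 13.1 points.
- Gains swapped: (20 + 7.5)/175 = 15.7 becomes (20 + 4.5)/145 = 16.9 points.
- Equal gains: no change.

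**If severe survivors take part less often.** In the central case the prevalence effect cancels when (75 + 50f)/(75 + N) = 125/575, where f is turnout among severe survivors. With N = 400, f = 57% (overall 80%). With N = 325, f = 24% (overall 65%). Below these values PPV is understated. For example, N = 400 with f = 50% gives q = 100/475 = 21.1% and PPV 65.1%, against 66.0%.

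**The case against.** - **Terminations.** A reader might infer that every non-survivor enters as a poor outcome. The document does not support that, because terminations are adjudicated. The cohort of 832, less 500 survivors and 50-100 non-survivors, leaves about 232-282 pregnancies that were terminated or have unknown outcome. If terminations with a poor prognosis are left out, poor outcomes could be under-represented relative to everyone counselled. This stands, and it limits the point to the non-termination cohort.
- **Deaths must be found.** The check against national records is made only where available, with medical notes as the fallback. Inclusion of deaths may therefore fall a little short of complete.
- **Sensitivity and the headline comparison.** A reader might infer that sensitivity is inflated or that MR is favoured over USS. Neither follows. The first would need deaths to have received a poor prognosis more often than severe survivors, and no passage says so. The paired difference can move either way or not at all.
- **Direction.** Low turnout among severely impaired survivors can cancel or reverse the PPV effect. This stands. It is also a reason not to rely on pooled raw values.
- **Precision.** With 325 survivors, about 0.7 × 107.5 + 0.1 × 292.5 = 104.5 cases are called poor, so the 95% half-width for PPV is about 9 points, wider than the bias. True, but the interval would be centred in the wrong place for an avoidable reason.
- **Silence.** The protocol never says the estimates are unweighted, and an SAP, not at hand, may add weighting. It also limits loss through the ASQ and through postal or telephone questionnaires. Even so, the protocol itself fixes who enters, which measures are reported, a table of raw counts, and a check that is only descriptive.

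**Conclusion.** The point holds in a limited form. Within the non-termination cohort, and if survivor participation is unrelated to outcome, the planned pooling overstates the PPV of a poor prognosis and understates the NPV. In the central case the errors are about 3 points (400 survivors) or 6 points (325 survivors) for PPV, and about 1-2 points for NPV. The severity rate, sensitivity and specificity behind these sizes are assumptions. The survivor count, the range for deaths and the 400 are the plan's own.

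Pooled sensitivity depends on turnout with no fixed direction, specificity is unaffected under the same assumption, and the bias in the paired MR-USS difference has no fixed sign. The documents do not show that the results will flatter prenatal prognosis in general or MR in particular. The change is worth making before analysis, because predictive values bear directly on Project 2's aim and the planned check does not correct them.

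**What to change.** In section 7, Analysis of Project 2:

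1. State the population to which the estimates refer, and give results with and without adjudicated terminations.
2. Say whether the 400 cases include non-survivors.
3. Weight each assessed survivor by the inverse of the estimated probability of being assessed, given prenatal prognosis, diagnosis and site. Give included non-survivors weight 1.
4. Report weighted sensitivity, specificity, PPV and NPV for MR and USS, with bootstrap intervals that re-estimate the weights in each resample.
5. Show survivors-only results beside the pooled ones.
6. Keep the consenter-refuser comparison as description, and extend it to survivors lost through age, exclusion or non-contact.

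The cost is analysis wording and code, with slightly wider intervals. No new data are needed, since prenatal prognosis and diagnosis were collected in the main study. Weighting does not remove bias from participation that depends on unmeasured outcome, which is why the survivors-only results and a stated limitation are still needed.
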